Inclusion/Exclusion criteria	
Inclusion Criteria:
 
 • Patient must be 18 years of age or older • Patient must have been treated with either Knee Spanning or Damage Control FastFrame External Fixation System according to the indications stated in this protocol* 
Exclusion Criteria:
 
 • Patient has an active or suspected infection • Conditions that limit the patient's ability and/or willingness to follow instructions during the healing process • Inadequate skin, bone, or neurovascular status • Patient is a prisoner • Patient is pregnant and/or breastfeeding • Patient is a known current alcohol and/or drug abuser in the opinion of the Investigator • Patient has a mental or neurologic condition that will not allow for proper informed consent and/or participation in follow-up program in the opinion of the Investigator 
*EEA Indications (a subset of the cleared US indications): The FastFrame External Fixation System – Knee Spanning Kit is indicated for use in treatment of long bone (distal femur, proximal tibia) fractures. Specifically, the system is intended for temporary stabilization of open or closed fractures about the knee, typically in the context of polytrauma or where open or alternative closed treatment is undesirable or otherwise contraindicated.
 
The FastFrame External Fixation System – Damage Control Kit is indicated for use in treatment of mid-shaft long bone (femur, tibia) fractures. Specifically, the system is intended for temporary stabilization of open or closed fractures of the femur and tibia, typically in the context of polytrauma or where open or alternative closed treatment is undesirable or otherwise contraindicated.

Study Design	Prospective enrollment, prospective follow-up, single cohort study
Clinical Phase	Postmarket
Sample Size	Considering a 95% device success rate (5% device related complications) and a 10% non-inferiority margin, 60 subjects with a follow-up are required. With an estimated lost to follow-up/subject withdrawal rate of 10%, 66 subjects will have to be enrolled.
Length of Study	3 years (2 years of enrollment plus follow-up until exchange with another device) A follow-up visit will be completed at the time of exchange from FastFrame System to another device. Typically, this exchange occurs 2 to 4 weeks after injury.

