This is a PMCF study designed to collect and evaluate outcome measures and adverse event data. A maximum of three sites will contribute to this study. Each Investigator will be skilled in external fracture stabilization and experienced in implanting the devices included in this study, as determined by the Sponsor.

Each Investigator will be responsible for obtaining IRB approval as required prior

to conducting the study. In order to avoid potential selection bias, each Investigator will offer study participation to each consecutive eligible patient presenting need for temporary stabilization with the FastFrame External Fixation System - Knee Spanning or Damage Control Kits. Eligible candidates who express interest in study participation will be offered **Informed Consent**. All potential study subjects will be required to participate in the Informed Consent process and will not be considered enrolled in the study until the candidate has signed and dated the IRB approved **Informed Consent** and the study device has been implanted.

VIII. Study Population

A maximum of three (3) sites in the United States will contribute to this study. No randomization will take place, as all subjects must receive the study device that best treats their clinical need.

The study population for primary statistical analysis will be comprised of all enrolled subjects who satisfy the Inclusion/Exclusion Criteria outlined in the protocol. In order to avoid potential selection bias, each Investigator will offer study participation to each consecutive eligible patient presenting as a candidate. Eligible candidates who express interest in study participation will be offered **Informed Consent**. Inclusion/Exclusion Criteria should not be evaluated until the **Informed Consent** has been completed.

Inclusion Criteria

- Patient must be 18 years of age or older
- Patient must be treated with either the Knee Spanning or Damage Control FastFrame External Fixation System according to the indications stated in this protocol*

*EEA Indications (a subset of the cleared US indications):

The FastFrame External Fixation System – Knee Spanning Kit is indicated for use in treatment of long bone (distal femur, proximal tibia) fractures. Specifically, the system is intended for temporary stabilization of open or closed fractures about the knee, typically in the context of polytrauma or where open or alternative closed treatment is undesirable or otherwise contraindicated.

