All surgeries will take place following the standard, approved surgical technique. During the course of the surgery, a **Surgical Device** CRF must be completed documenting the part and lot numbers of the implants. The FDA cleared or other local government regulatory body approved instructions for use and surgical technique must be followed for this product. Please refer to the latest versions of these documents on the Zimmer Biomet website, contact your local Clinical Study Manager, or contact a Zimmer Biomet sales associate for additional details. The following operative data will be collected on the following CRFs:

- **Operative Record**
- **Surgical Device**
- **Protocol Deviation, if applicable**
- **Adverse Event Report, if applicable**
- **Physician Imaging Assessment**
- **Photographs of study device in two (2) planes (A/P and lateral)**

Photographs will be stored in the Subject Binder as part of their casebook. Please write the Subject Case ID Number, Subject Initials, and Date (YYYY-MM-DD) on the photographs. If an adverse event occurs, an **Adverse Event Report** CRF will also be completed. See Management of Incurrent Events for additional details. Reason(s) for study completion must be documented on the **Study Completion** CRF.

Post-Operative Follow-Up Procedure

Post-operative clinical assessment will be conducted at the device exchange follow-up visit after the procedure. The device exchange of a FastFrame External Fixation Kit typically occurs 2-4 weeks after surgery. The following

CRFs will be collected at the follow-up visit when the study device is removed from the subject:

- **Physician Follow-Up Assessment**
- **Protocol Deviation, if applicable**
- **Adverse Event Report, if applicable**
- **Physician Imaging Assessment, if required**
- **Photographs of study device in two (2) planes (A/P and lateral), if required**
- **Study Completion**

Subjects will be followed post-operatively until the FastFrame External Fixation Kit is exchanged with another device or unless the primary endpoint is reached prior. Unless the study is otherwise closed, data will continue to be collected until the subject completes the study per the protocol, voluntarily withdraws from the study, is withdrawn from the study by the Investigator, is lost to follow-up, undergoes revision to remove a study device (does not include device removal as part of standard treatment), or expires.

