All components removed outside of standard of care should be promptly returned to Zimmer Biomet for analysis. The Investigator or Designee must notify the Clinical Study Manager prior to the return of any device. Properly prepared components are to be sent to the following address:

Zimmer Biomet
Attention: Product Services Department
[name]
[name] USA

Investigator Withdrawal

The Investigator can choose to withdraw a subject from the study if it is deemed to be in the subject's best interest or the subject does not consent to continue in the study after being informed of changes in the research that might affect them. The reason for the Investigator's withdrawal of the subject must be documented on the **Study Completion** CRF.

Subject Withdrawal

Study subjects may choose to withdraw from the study at any time, for any reason. If possible, a final evaluation will be completed for any subject whom no longer wishes to participate in the study. The reason for the subject withdrawal must be documented on the **Study Completion** CRF.

Lost to Follow-up

Subjects will be considered lost to follow-up after they have missed their follow-up visit and a reasonable number of attempts to locate and evaluate them have failed. All attempts of contact have to be documented on the **Study Completion** CRF and in particular, the reason should be documented. Patients lost to follow-up will not be replaced within the study.

Protocol Deviations

The Investigator should not deviate from the agreed upon protocol unless it is to eliminate hazard to the patient. However, any deviation from the protocol has to be documented on the **Protocol Deviation** CRF along with an explanation for the

deviation and reported to the Sponsor. Each significant deviation will be reported to the IRB, if applicable, within the appropriate deadlines stipulated by the appropriate regulatory authorities. Significant deviations are defined as those impacting or potentially impacting patient safety.

Investigator disqualification criteria leading to exclusion from the clinical study include fraud, misconduct, and serial non-compliance.

Study Termination

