Statistical methodology will consist of summarizing collected data descriptively. Categorical data (i.e., gender or race) will be summarized using counts and percentages, and 95% CI, over the time periods of interest. Continuous data, such as age, will be summarized by using means, medians, standard deviation, minimum, maximum, and 95% CI over the time periods of interest. Implant survival will be summarized using a Kaplan-Meier method and presented with rates (as percentages) and confidence intervals.

Sample Size

Calculation of sample size is based on previously published literature involving longitudinal data collection on temporary external fixation. Assuming a power level of 80% and an alpha level of significance of 0.05 ($\alpha = 0.05$), calculations were performed in order to determine the sample size needed for study significance using the following hypothesis test:

The hypothesis will be tested by the exact binomial test:

$$H_0: E_1 - E_0 \leq -\delta E$$

$$H_a: E_1 - E_0 > -\delta E$$

where:

$E_0 = 95\%$, the expected success rate

E_1 = the success rate in the FastFrame System treatment group

$\delta E = 0.10$, non-inferiority margin

In addition, one-sided 95% exact confidence Interval (CI), lower limit of the success rate, will be calculated.

Based on the hypothesis test above, 60 subjects will provide approximately 80% power for the one-sided exact binomial test at 0.05 significant level. The sample size was calculated using SAS for Windows version 9.4.

It was determined that the complication rate of devices comparable to the FastFrame External Fixation System is approximately 5%. Utilizing this figure, the power, and alpha level of significance, a sample size total (without any subjects becoming lost to follow-up) of 60 was obtained. Finally, in order to maintain a sample size large enough for statistical significance an estimated, 90% subject return rate is assumed for the duration of the device exchange follow-up visits. These lost to follow-up patients increase the sample size requirements to 66 subjects (after rounding up).

Visit	Subjects remaining in the study
Baseline	66
Follow-Up	60

XVI. Quality Control & Quality Assurance

The study is conducted in accordance with the Declaration of Helsinki and the ISO 14155:2020 and Regulation (EU) 2017/745.

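### Does the lack of a counting rule for subjects who leave before device exchange undermine the primary exact binomial test?

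*Combined protocol and SAP*

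**What the plan says.** Section VIII (Study Population) defines the primary analysis set: "The study population for primary statistical analysis will be comprised of all enrolled subjects who satisfy the Inclusion/Exclusion Criteria outlined in the protocol". Under Section X (Subject Enrollment), enrolment requires signed consent and an implanted device, with no condition on follow-up.

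The Synopsis sizes the study on completers: "Considering a 95% device success rate (5% device related complications) and a 10% non-inferiority margin, 60 subjects with a follow-up are required". Section XV (Sample Size) agrees: "60 subjects will provide approximately 80% power for the one-sided exact binomial test at 0.05 significant level". Its table shows 66 subjects at baseline and 60 at follow-up.

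Section X (Post-Operative Follow-Up Procedure) says "Subjects will be followed post-operatively until the FastFrame External Fixation Kit is exchanged with another device or unless the primary endpoint is reached prior", and lists how data collection may end sooner: a subject "voluntarily withdraws from the study, is withdrawn from the study by the Investigator, is lost to follow-up, undergoes revision to remove a study device", or dies. Section XI (Lost to Follow-up) adds "Patients lost to follow-up will not be replaced within the study".

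The nearest text on incomplete follow-up is in Section XV (General Statistical Methods): "Implant survival will be summarized using a Kaplan-Meier method and presented with rates (as percentages) and confidence intervals". That is a descriptive summary and is not linked to the hypothesis test.

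**The concern.** A binomial test needs a yes-or-no outcome for everyone in its denominator. Read literally, Section VIII keeps all 66 subjects, yet the plan itself expects about 6 of them to have no follow-up visit. It does not say whether those subjects are successes, failures or excluded.

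The study has a single arm, and the sponsor or its designee analyses it. An unwritten rule could therefore be settled after the outcomes are known, and identical data could pass or fail on that choice. For example, with 8 subjects lost and 4 failures observed, counting the lost as event-free gives 62/66, which passes, while leaving them out gives 54/58, which fails. If lost subjects were counted as failures, the planned 6 losses alone would exceed the 4 failures that the test tolerates.

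**Working it through.** **Inputs.** Expected success rate 95%, margin 10 points, one-sided alpha 0.05, 60 analysed (Section XV); 66 enrolled and 10% loss (Synopsis). The null success rate is 0.95 − 0.10 = 0.85.

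**Step 1: reproduce the plan's figure.** Let F be the number of failures among n subjects. The limit c is the largest value with P(F ≤ c | n, 0.15) ≤ 0.05. Power is P(F ≤ c | n, 0.05).

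| n | c | Actual one-sided error | Power |
|---|---|---|---|
| 58 | 3 | 0.0187 | 0.6703 |
| 59 | 4 | 0.0469 | 0.8281 |
| 60 | 4 | 0.0424 | 0.8197 |
| 66 | 4 | 0.0226 | 0.7659 |

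At n = 60 the result is 82.0%, so the stated figure of about 80% is correct. The exact lower limit for 56/60 is 0.854, just above 0.85.

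**Step 2: compare the two natural rules.** Let L of the 66 leave with no recorded event.

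- *Left out:* n = 66 − L, with the limit c for that n.
- *Event-free:* n = 66, so at most 4 failures among the 66 − L observed.

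The limit is 4 for every n from 59 to 67. For L = 0 to 7, n = 66 − L runs from 66 down to 59, so both rules allow exactly 4 observed failures and always reach the same verdict. At the planned L = 6, both have power 0.8197 and error 0.0424.

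**Step 3: find where they part.** At L = 8, n = 58 and the left-out limit drops to 3. The rules then disagree only when there are exactly 4 failures among 58:

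- at 95% true success, P(F = 4 | 58, 0.05) = 0.166;
- at 85% true success, P(F = 4 | 58, 0.15) = 0.033.

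In that case the lower limits are 0.867 for 62/66 and 0.849 for 54/58. The event-free rule's error at L = 8 is P(F ≤ 4 | 58, 0.15) = 0.0519.

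**Step 4: average over the number lost.** Assume each subject is lost independently (the documents do not say this), so L ~ Binomial(66, d).

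- At d = 10% the expected loss is 66 × 0.10 = 6.6, and P(L ≥ 8) = 0.339.
- At d = 10% the verdicts differ with probability 0.055 at 95% true success and 0.013 at 85%.
- The average error of the event-free rule is 0.033, 0.046 and 0.065 at d = 5%, 10% and 15%.
- Average power with leavers left out is 0.793, 0.770 and 0.724 at the same loss rates.

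**Step 5: count leavers as failures.** The pass condition becomes at most 4 − L observed failures, so a pass is impossible from L = 5. At L = 6 even 60/66 fails (lower limit 0.828, p = 0.117).

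**The case for a change.** The strongest contrary case is that Section VIII is the only sentence defining the primary population, and it does not restrict the analysis to completers. The reference to 60 subjects with follow-up is a sizing statement, so a completers analysis is implied but never stated. Eight or more losses are not remote (34% under independent 10% loss). Conditional on that, the two lenient rules can disagree and the event-free rule slightly exceeds its nominal error. One sentence would settle the matter.

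The textual reading stands, and so does the divergence from 8 lost. Several things limit its weight.

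- The subjects affected are few. Those who reach the primary endpoint have an observed outcome (Section X). Early component removal requires an adverse event report, and a final evaluation is sought where possible from those who withdraw (Section XI). Consent may be given as late as the follow-up visit (Section X), and a subject consented then cannot be lost beforehand. What remains is withdrawal, loss or death with no device event on record.
- The failure rule produces the dramatic result, but no section suggests it, and a sponsor choosing after the fact would have no reason to adopt it.
- The available remedies gain little. A known-outcome denominator has its own bias. If 6 leavers each carry a 5% event risk and enter only when they had an event, mean observed success falls from 95.0% to 94.5% and power from 82.0% to 76.6%. Leaving them all out could instead hide events. A sensitivity analysis with missing counted as failure must fail once 5 are lost, so at the planned loss its verdict is known in advance. Restating the power would correct nothing, because the figure at 60 is right.

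**Conclusion.** No change to the plan follows. Sizing on 60 evaluable subjects and enrolling 66 is ordinary practice, and the power claim reproduces (82.0% at n = 60). The missing rule is a detail that an analyst would fill sensibly: subjects with a recorded device event count as failures, those with no event and no follow-up are left out, and their number is reported. Counting them as event-free would give the same verdict for any loss up to 7 of 66.

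The residual exposure is a 5.5% chance of differing verdicts at 95% true success and 1.3% at 85%. The more lenient rule's average one-sided error is 4.6%. These three figures assume independent loss at the planned 10%, unrelated to outcome, and one case per subject. If loss ran nearer 15%, the event-free rule's average error would rise to 6.5%. Leaving subjects out would keep the error below 5% but reduce average power to 72.4%. That cost comes from losing more subjects than planned, and a counting rule would not remove it.

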The management of orthopaedic polytrauma patients has developed greatly since the 1970s, when patients were deemed incapable of undergoing surgery³. In recent years, the use of temporary stabilization of fractures has been used with the goal to decrease operative time³, blood loss³, and the “second hit” inflammatory response from definitive surgical fixation². External fixators, a type of device intended for temporary stabilization, are typically made up of a combination of a frame, clamps, pins, and bars that properly stabilize and support the injured limb¹. In order for this stabilization to occur, the fractured bones are adjusted to reduce the fracture and the bars are connected to maintain the reduction¹. Unlike typical external fixators, the FastFrame External Fixation frames are pre-assembled and are designed for simplicity in the operating room. Each kit includes clamp bodies, pins, and telescoping bars that allow for proper reduction and rigid external fixation. This study will document the clinical outcomes of

trauma patients who require the use of the FastFrame External Fixation System - Knee Spanning and Damage Control kits legally manufactured by Zimmer, Inc.

VI. Study Objectives

The objective of this observational, prospective study is to confirm safety and performance of the FastFrame External Fixation System and corresponding instrumentation. The endpoints are defined to include the following:

Primary Endpoints

- Frequency and incidence of device-related adverse events and device deficiencies before the FastFrame External Fixation System is exchanged by another device (i.e. plates, screws, etc.). Refer to Section XII for additional details related to adverse event classification and device deficiencies.

Examples of device-related adverse events and device deficiencies include:

- Pin breakage and/or loosening requiring surgical intervention (i.e. pin removal or exchange) before planned exchange of the complete frame by another device
- Frame component failure (i.e. loosening, breakage, etc.) leading to clinically unacceptable loss of stability requiring unplanned readjustment or replacement of the frame

Secondary Endpoints

- Adverse events that occur between application of the FastFrame External Fixation System and exchange with another device that do not fall within the primary endpoint. Refer to Section XII for additional details related to adverse event classification.

VII. Study Design and Endpoints

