The FastFrame External Fixation System – Damage Control Kit is indicated for use in treatment of mid-shaft long bone (femur, tibia) fractures. Specifically, the system is intended for temporary stabilization of open or closed fractures of the femur and tibia, typically in the context of polytrauma or where open or alternative closed treatment is undesirable or otherwise contraindicated.

Exclusion Criteria

- Patient has an active or suspected infection
- Patient has conditions that limit their ability and/or willingness to follow instructions during the healing process
- Patient has inadequate skin, bone, or neurovascular status
- Patient is a prisoner
- Patient is pregnant and/or breastfeeding
- Patient is a known current alcohol and/or drug abuser in the opinion of the Investigator
- Patient has a mental or neurologic condition that will not allow for proper Informed Consent and/or participation in follow-up program in the opinion of the Investigator

IX. Study Device Information

The FastFrame External Fixation System Knee Spanning and Damage Control Kits are single-use external fixators that are sterile packed with all the required components (i.e., frame, pins, driver, tissue sleeve, and lockout tab). The device indications and contraindications for use can be found on the applicable package inserts. Surgical procedures involved in the use of FastFrame are located on the Zimmer Biomet website.

The following components and materials, used in both FastFrame Kits, have direct human tissue contact during the surgical procedure:

- 5mm Pin – 316L Stainless Steel
- Tissue Trocar – ULTEM® (Black)
- Tissue Sleeve Shaft – 304 Stainless Steel

These materials were tested for cytotoxicity, sensitization, intracutaneous reactivity, and acute systemic toxicity. The test results concluded that these materials are biocompatible and toxicologically safe for use as materials in orthopaedic surgery.

X. Study Procedures

All procedures are to be conducted in accordance with the current surgical techniques supplied to all Investigators in the clinical study and found on the Zimmer Biomet website.

Offer Study Participation

Study participation will be offered to each consecutive eligible patient presenting as a potential candidate for the study. Eligible candidates who express interest in study participation will be offered **Informed Consent**.

Informed Consent Process

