Informed Consent will be completed by patients who are able to consent themselves or if unable, have a proxy available. The patient will be given an adequate amount of time to read the consent and ask questions to the investigator and/or research staff. If the patient agrees to participate in the study, he/she will sign the consent form. If a patient is unable to consent for him/herself due to the need for immediate surgical intervention, a proxy signature may be used to consent on the patient's behalf. The following individuals may serve as a proxy on behalf of the patient during the Informed Consent process: legal guardian, proxy health care agent, or a close family member of the patient. The relationship of the proxy to the patient must be documented on the **Informed Consent Log**. If the patient becomes able to consent himself or herself at any point in time, a re-consent must occur with the patient's signature. Due to the immediate surgical intervention regarding the study operation, Informed Consent can be obtained after surgery, but no later than the follow-up visit defined in this protocol.

Informed Consent/Enrollment Log

An **Informed Consent/Enrollment Log** will be maintained at the site throughout the course of the study. The purpose of the log is to provide documentation that all enrolled study subjects and/or proxies as defined in the Informed Consent Process section of this protocol underwent the Informed Consent process, signed and dated the IRB approved **Informed Consent**, and were provided with a copy of the fully executed consent with all required signatures. All candidates who sign and date the approved **Informed Consent** for the study must be entered in the

log. If a subject signs and dates additional Informed Consent(s) after enrollment (i.e., due to a protocol amendment, protocol revisions, re-consent after surgery, etc.), subsequent signings will also be recorded in the log. If a proxy signature is used, the relationship of the proxy to the patient must be documented. The **Informed Consent/Enrollment Log** will be filed in the site Regulatory Binder for the study.

Subject Enrollment

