Once the **Informed Consent** has been signed and dated by the subject (or proxy as defined in the Informed Consent Process section of this protocol) and a FastFrame System has been implanted, the subject will be considered enrolled in the study. A unique case identification number (Case ID) will be assigned to each participating subject (bilateral subjects will be assigned a unique case ID number for each temporary stabilization procedure). This unique case ID number will be used throughout the study for identification. Case ID numbers will be assigned consecutively in ascending order per site, with the starting number for a given site defined by the Sponsor.

Monitoring Log

The **Site Monitoring Visit Log** will be maintained throughout the course of the study. The log will contain the visit date, monitor name/signature and the purpose of the visit (i.e. site initiation, onsite interim monitoring (as applicable), site closeout, etc.). The **Site Monitoring Visit Log** will be filed in the site Regulatory Binder for the study.

Delegation of Authority/Site Signature Log

A **Delegation of Authority/Site Signature Log** will be maintained throughout the study and will contain the names, initials, signatures, and study responsibilities of all site personnel and designees involved in the study procedures and data collection. The Investigator is responsible to sign and date the log after any updates to the log to acknowledge the change(s). The **Delegation of Authority/Site Signature Log** will be filed in the site Regulatory Binder for the study.

Baseline Procedure

Subjects will be enrolled prior to undergoing a procedure using the FastFrame External Fixation System, therefore allowing for the capture of baseline data to be

collected on the following CRFs:

- **Inclusion/Exclusion Criteria**
- **Demographic Evaluation**
- **Protocol Deviation, if applicable**

Operative/Immediate Post-Operative Procedure

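### The primary safety test leaves out treated subjects judged ineligible, possibly after a device event is known, and no all-treated analysis is planned to show whether this changed the result

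*Combined protocol and SAP*

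**What the plan says.** **Objective and endpoint.** Section VI states: "The objective of this observational, prospective study is to confirm safety and performance of the FastFrame External Fixation System and corresponding instrumentation". The primary endpoint is "Frequency and incidence of device-related adverse events and device deficiencies before the FastFrame External Fixation System is exchanged by another device".

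**Analysis set.** Section VIII: "The study population for primary statistical analysis will be comprised of all enrolled subjects who satisfy the Inclusion/Exclusion Criteria outlined in the protocol". Section XV gives the exact binomial test and the one-sided 95% lower limit but names no analysis set. Neither section plans an all-treated or sensitivity analysis.

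**Enrolment.** Section X (Subject Enrollment) says that once consent is signed "and a FastFrame System has been implanted, the subject will be considered enrolled in the study". Section VII agrees.

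**Timing.** Section VIII says that "Inclusion/Exclusion Criteria should not be evaluated until the" consent form is complete. Section X (Informed Consent Process) adds: "Informed Consent can be obtained after surgery, but no later than the follow-up visit defined in this protocol". Section X (Baseline Procedure) says instead that subjects are enrolled before the procedure. The two statements are not reconciled.

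**Criteria.** Some exclusions are explicitly matters of opinion, for example "Patient is a known current alcohol and/or drug abuser in the opinion of the Investigator". Others have no threshold, for example "Patient has inadequate skin, bone, or neurovascular status".

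**The concern.** Every enrolled subject has, by definition, been treated. The eligibility condition in Section VIII therefore cannot screen out untreated people. All it can do is take treated subjects, with their outcomes, out of a device-safety result.

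That would be of little consequence if eligibility were always fixed before the outcome could be known. The consent provision means it need not be. A subject may have the frame fitted, have a pin or frame problem, consent at the exchange visit, and only then be assessed against criteria that partly depend on opinion. If that subject is ruled ineligible, the failure leaves both numerator and denominator of the primary test. No planned analysis shows what the result would have been with the subject included. Because the test tolerates only a handful of failures, one such decision can settle the study's conclusion.

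**Working it through.** **Inputs (Section XV and the Synopsis).** Expected success 95%, margin 10 points, so the null success rate is 95% − 10% = 85% (15% failure). One-sided alpha 0.05, exact binomial test, 60 evaluable subjects, about 80% power, 66 enrolled.

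**Step 1: reproduce the plan's figure.** Let X be the number of failures. The test passes if P(X ≤ x | n, 0.15) ≤ 0.05 at the observed x.
- n = 60, x = 4: 0.0001 + 0.0006 + 0.0032 + 0.0110 + 0.0275 = 0.0424, pass.
- n = 60, x = 5: 0.0424 + 0.0544 = 0.0968, fail.
- So at most 4 failures are allowed. Power at 5% failure is P(X ≤ 4 | 60, 0.05) = 0.820. The stated 60 subjects and roughly 80% power reproduce.

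**Step 2: remove one failing subject.** The one-sided 95% exact lower limit for s successes in n is the 5th percentile of Beta(s, n − s + 1).

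| Data | p | Lower limit | Result |
|---|---|---|---|
| 5 failures in 60 | 0.0968 | 83.3% | fail |
| 4 failures in 59 | 0.0469 | 85.15% | pass |
| 5 failures in 66 | 0.0562 | 84.7% | fail |
| 4 failures in 65 | 0.0252 | 86.5% | pass |

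The same one-subject change of result occurs at every n from 60 to 67 when failures are one above the limit. It does not occur at n = 59, because 4 failures in 58 give p = 0.0519.

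**Step 3: how often the data sit there.** At n = 60, P(X = 5) is 0.10 at 95% true success and 0.054 at 85%. If one failing subject were removed whenever that helped, the false-pass rate would go from 0.0424 to 0.0968 at n = 60, and from 0.0226 to 0.0562 at n = 66. This is the bound for removing a single subject.

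**Step 4: false-pass rate under assumed exclusion rates.** The documents give no exclusion rate, so these are assumptions. Let a be the chance that a failing subject is ruled ineligible and b the same chance for a non-failing subject. Sum over f failures ~ Bin(n, 0.15), dropped failures d ~ Bin(f, a) and dropped non-failures e ~ Bin(n − f, b). Count a pass when f − d is within the exact limit for n − d − e subjects.

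| a / b | n = 60 | n = 66 |
|---|---|---|
| 0 / 0 (base) | 4.2% | 2.3% |
| 5% / 0 | 5.5% | 3.3% |
| 10% / 0 | 6.6% | 4.6% |
| 20% / 0 | 9.4% | 9.0% |
| 20% / 10% | 5.6% | 5.9% |
| 10% / 5% | 3.6% | 4.5% |
| 20% / 20% | 2.8% | 3.1% |

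The rows with b = 0 describe exclusion driven by the outcome. Rows with b above zero are closer to eligibility judged without knowledge of events.

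**The case against.** **Ineligible enrolled subjects should be rare.** Participation is offered to consecutive eligible patients, and the eligibility form is listed as baseline data. A footnote to the Section IV table also says that some forms are conditions of enrolment, though which ones cannot be read from the text available here. This lowers the expected number. It does not close the gap: Section VIII would not need the eligibility condition if no ineligible subject could be enrolled, and formal evaluation still waits for a consent that may come late.

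**The events are not lost.** Section XI requires adverse events to be documented throughout, and Section XV summarises collected data descriptively, neither limited to eligible subjects. That is correct, and it is why the fix needs no new data. The formal test and limit would still leave those subjects out.

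**An eligible-only set suits the labelled use.** The inclusion criteria restrict the study to use within the stated indications, so this is a legitimate primary set. That stands, and the fix keeps it.

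**Stronger readings.** A reader might infer that the rule doubles the false-pass rate. The 9.4% at n = 60 needs 20% of failing subjects and no non-failing subjects to be excluded, which is the outcome-driven extreme. A reader might also infer upward bias even when eligibility is judged promptly at baseline, on the ground that the criteria predict pin or frame problems. The documents do not state that link. When non-failing subjects are dropped too, the rate stays near or below 6%, and at n = 60 it can fall below the base. Nothing in the documents suggests that selective exclusion is intended or has occurred.

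**Conclusion.** The point holds as a gap in the analysis plan. The primary test of a safety endpoint can lose treated subjects on judgements made after a device event is known, and no planned analysis would show the effect.

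One exclusion can turn a fail into a pass only when failures are exactly one above the limit, as with 5 in 60. That is an occasional situation, but the probability of about 10% applies at the plan's own expected success rate. No single figure can be given for the average effect on the false-pass rate. Over the assumptions tried it runs from 2.8% to 9.4% at n = 60 (base 4.2%) and from 3.1% to 9.0% at n = 66 (base 2.3%). Whether it exceeds 5% depends on how selectively failing subjects are excluded, which the documents do not let us estimate.

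**What to change.** In Sections VIII and XV:
- Add the exact binomial test and one-sided 95% lower limit on all enrolled subjects treated with a FastFrame kit, reported beside the eligible-only result.
- List each enrolled subject judged ineligible, with the criterion, the date of the eligibility decision and the outcome.
- State that any disagreement between the two results will be discussed in the conclusion.

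It is not necessary to make success depend on both results exceeding 85%. That would add a second success condition and could only lower the power of 0.82 at n = 60, a trade-off the sponsor would have to weigh separately.

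The cost is one more table, a short listing and a few sentences, using data already collected. The downside for the sponsor is that the all-treated success rate may be slightly less favourable.
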